### **AE reporting for CT.gov**

For the legal requirements of clinicaltrials.gov, two required tables on treatment emergent adverse events which are not serious adverse events with an incidence greater than X% (X will

be selected prior to final database lock)\* and on treatment emergent serious adverse events and SAE suspected to be related to study treatment will be provided by SOC and PT on the safety set population.

If for a same patient, several consecutive AEs (irrespective of study treatment causality, seriousness, and severity) occurred with the same SOC and PT:

- a single occurrence will be counted if there is  $\leq$  1 day gap between the end date of the preceding AE and the start date of the consecutive AE
- more than one occurrence will be counted if there is  $>$  1 day gap between the end date of the preceding AE and the start date of the consecutive AE

For occurrence, the presence of at least one SAE / SAE suspected to be related to study treatment / non SAE has to be checked in a block e.g., among AE's in a  $\leq$  1 day gap block, if at least one SAE is occurring, then one occurrence is calculated for that SAE.

The number of deaths resulting from SAEs suspected to be related to study treatment and SAEs irrespective of study treatment relationship will be provided by SOC and PT.

These summaries will be provided only after full study completion.

\*Note: the X% has been chosen as 5% before the final database lock.

### **2.7.1.1 Adverse events of special interest / grouping of AEs**

The number and percentage of participants with adverse event of special interest (AESI) will be summarized for each topic for:

- TEAE by study part, treatment group and PT

In final analyses, OLS will be used for the summary tables of extension part data. Besides, summary tables for overall study will also be provided using SAF. In core part analyses, summary of TEAE by treatment group, PT and maximum severity and of TESAE by treatment group and PT will also be provided. PTs will be sorted in descending order of frequency in the total column. If a participant reported more than one adverse event with the same PT, the AE will be counted only once. If a participant reported more than one AE within the same AESI, the participant will be counted only once at that AESI.

Adverse event of special interest will include the following:

- Hepatotoxicity
- Injection site reaction

For injection site reaction, separate listing will be provided for participants with injection site reaction AE in both core part analyses and final analyses. The time to the first injection site reaction TEAE will also be summarized by treatment group and study part using the following categories: No ISR,  $\leq$ 4h,  $>$ 4h to  $\leq$ 12h,  $>$ 12h. The time (hours) to the event will be calculated from the most recent administration of study drug. The duration of the first injection site reaction TEAE will also be summarized by treatment group and study part using the following categories: No ISR,  $\leq$ 4h,  $>$ 4h to  $\leq$ 7 days,  $>$ 7 days to  $\leq$ 14 days,  $>$ 14 days. Total number of TEAE at the injection site per participants will be summarized in categories (e.g. 1, 2, 3, and  $>$ 3 etc.)

by treatment group and study part. In final analyses, OLS will be used for the summary tables of extension part data. Besides, all summary tables of injection site reaction will also be provided for overall study using SAF.

Case Retrieval Strategy (CRS) will be used to determine the MedDRA search criteria to be used to identify the AESI. The CRS listing will be provided.

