- The overall study duration is approximately 374 days but can vary depending on individual screening and the visit window.
- Participants will receive inclisiran/placebo subcutaneous injections on Day 1, Day 90, Day 180. And all participants will receive inclisiran treatment on Day 270.
- Visits will be on Day 1, Day 30, Day 90, Day 150 (primary endpoint), Day 180 (end of core part, EOC), Day 210, Day 270, Day 330 and Day 360 (EOS).

Treatment of interest

For primary estimand, the treatment of interest is inclisiran sodium 300 mg s.c. at Day 1 and Day 90 as monotherapy (no other lipid lowering therapy) comparing to matching placebo s.c. at Day 1 and Day 90 as monotherapy, regardless of study treatment discontinuation.

Number of Participants:

Approximately 200 participants will be randomized 1:1 to inclisiran and placebo .

Key Inclusion criteria

- Written informed consent must be obtained before any assessment is performed
- Adults ≥ 18 and ≤ 75 years of age
- Fasting LDL-C value of ≥ 130 mg/dL but <190 mg/dL at screening
- Triglycerides ≤ 400 mg/dL at screening

- Categorized as low or moderate ASCVD risk by the 2016 Chinese guideline for the management of dyslipidemia in adults at screening
- No plan of introducing other lipid lowering therapy during the study participation

Key Exclusion criteria

- Use of any lipid-lowering therapy within 90 days prior to screening visit
- Previous exposure to inclisiran or any non-mAb PCSK9-targeted therapy, either as an investigational or marketed drug within 2 years prior to screening visit
- History of ASCVD
- Diabetes mellitus or fasting plasma glucose at screening \geq 7.0 mmol/L or glycated hemoglobin (hemoglobin A1c) (HbA1c) \geq 6.5%
- Active liver disease defined as any known current infectious, neoplastic, or metabolic pathology of the liver or unexplained elevations in alanine aminotransferase (ALT), aspartate aminotransferase (AST), >3 x the upper limit of normal (ULN), or total bilirubin >2 x ULN at screening
- Estimated glomerular filtration rate (eGFR) $<$ 30 mL/min/1.73m² at screening

Treatment Groups:

At Day 1 (Baseline), all participants will be randomized 1:1 to one of the two treatment groups:

- **Inclisiran Group:** 100 participants. Treated with inclisiran sodium 300mg s.c. on Day 1, Day 90 and Day 270, and with matching placebo s.c. on Day 180.

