- **Control Group:** 100 participants. Treated with matching placebo s.c. on Day 1 and Day 90, and with inclisiran sodium 300mg s.c. on Day 180 and Day 270.

[figure not shown]
Steering Committee: Yes (see Section 10.1.4 Committees Structure)

Key words

Inclisiran, LDL-C, monotherapy

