At screening, participants will sign the Informed Consent Form (ICF) and their eligibility will be assessed through the review of study inclusion/exclusion criteria. The ICF must be signed before initiation of any study-specific procedures and assessments. If at the time of ICF signature the participant is not fasting, he/she has to return for the blood test in a fasting state. During the screening visit, the participant's ASCVD risk will be assessed under guidance of 2016 China lipid guideline([Zhao et al 2016](#)). The investigator must ensure each participant has not been treated with any lipid lowering therapy for at least 90 days prior to the screening visit, nor exposure to inclisiran or any other non-mAb PCKS9-targeted therapy 2 years prior to the screening visit. The screening period can be up to 14 days to allow adequate time for the eligibility evaluations. A participant who enters screening and is determined not eligible during the screening period or at the time of randomization will be considered a screen failure.

On Day 1 (Baseline), eligible participants who meet all inclusion and not meet any exclusion criteria will be randomized 1:1 to Inclisiran Group and Control Group. Study visits of core part will occur on Day 1 (baseline visit), Day 30, Day 90, Day 150 and Day 180. On Day 1 and Day 90 visits, inclisiran s.c. or placebo s.c. will be administered at the site by a healthcare professional. The primary endpoint will be assessed at Day 150. The EOC visit will be conducted on Day 180.

The extension part starts with a dose on Day 180 after all core part assessment are completed. In order to maintain the blind for the treatment group assignment, participants randomized to Control Group will receive inclisiran, while participants randomized to Inclisiran Group will receive placebo on Day 180. All participants will then receive inclisiran sodium 300 mg on Day 270, which will be the third dose of inclisiran for Inclisiran Group, and the second dose of inclisiran for Control Group. All injections will be administered at the site by a healthcare professional. The EOS visit (Day 360) will be the last visit of the study.

At Day 1 (Baseline), all participants will be instructed to comply with lifestyle adjustment according to clinical guidelines, including but not limited to diet and regular exercise. These instructions will be reinforced at every visit throughout the study.

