6.1.3 Treatment duration

The expected duration of the participant's involvement in the study will be approximately 374 days, which includes a screening period (14 days), a subsequent 180-day double-blind, placebo-controlled treatment period (core part), and a 180-day open label treatment period (extension part).

Participants may be discontinued from the study treatment earlier due to any reasons, at the discretion of the investigator or the participant. They will continue to be followed up in the study until EOS as per Assessment Schedule ([Table 1-2](#)).

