### 1.1 Study design

This study is designed as a randomized, double-blind, multi-center phase 3 trial, with a placebo-controlled period and an open label treatment period, to evaluate the efficacy and safety of inclisiran sodium 300mg s.c. in participants aged 18~75 years with low or moderate ASCVD risk and fasting low-density lipoprotein cholesterol (LDL-C) value of  $\geq 130$  mg/dL but  $< 190$  mg/dL who are not on any lipid lowering therapy.

The study design is depicted in [Figure 1-1](#). The study consists of 3 parts:

- **Screening:** a screening period of up to 14 days for all participants
- **Core Part:** a double-blind, placebo-controlled treatment period of 180 days in which eligible participants will be randomized 1:1 to receive either inclisiran sodium 300mg s.c. (Inclisiran Group) or matching placebo s.c. (Control Group) on Day 1 and Day 90. The end of core part (EOC) visit will be conducted on Day 180. The database lock for the core part is planned to occur after all randomized participants have completed the EOC visit (or have discontinued from the study before EOC). The primary endpoint analysis will be conducted after the database lock for the core part.
- **Extension Part:** an extended treatment period of 180 days. After all "Core part" study assessments are completed on Day 180, the extension part starts. In the extension, all patients randomized to inclisiran in the core part will continue on inclisiran while patients initially randomized to placebo will transit to inclisiran therapy. The extension part starts from a dose of study treatment on Day 180 (placebo in the inclisiran group and inclisiran for patients originally randomized to the control group). Thereafter, all participants will receive inclisiran sodium 300mg s.c. on Day 270. Treatment on Day 270 will be open-label. Participants and investigators/site staff will remain blinded to the original randomized treatment group assignment (inclisiran vs placebo) until final database lock. The EOS visit (Day 360) will be the last visit of the study.

**Figure 1-1** Study design

1. Participants who discontinue from study treatment should continue to attend the rest of the scheduled visits.

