2. Participants randomized to Inclisiran Group will be treated with inclisiran sodium 300mg s.c. on Day 1 and Day 90 and Day 270, and with matching placebo s.c. on Day 180. Participants randomized to Control Group will be treated with matching placebo s.c. on Day 1 and Day 90, and with inclisiran sodium 300mg on Day 180 and Day 270.
3. The end of core part visit. The database lock for the core part is planned to occur after all randomized participants have completed the EOC visit (or have discontinued from the study before EOC). The primary endpoint analysis will be conducted after the database lock for the core part.
4. Participants who discontinue from study should be scheduled for an Early Exit visit if they agree. This Early Exit visit is suggested to be scheduled at least 30 days after last injection. If not possible, to set an Early Exit visit as soon as possible is also acceptable.

On Day 1 (Baseline), approximately 200 eligible participants who meet all inclusion and not meet any exclusion criteria will be randomized 1:1 to Inclisiran Group and Control Group. Study visits of core part will occur on Day 1 (baseline visit), Day 30, Day 90, Day 150, and Day 180. On Day 1 and Day 90 visits, inclisiran s.c. or placebo s.c. will be administered at the site by a healthcare professional. The primary endpoint will be assessed at Day 150. The EOC visit will be conducted on Day 180.

The extension part starts with a dose on Day 180 after all core part assessments are completed. In order to maintain the blind for the treatment group assignment, participants randomized to Control Group will receive inclisiran, while participants randomized to Inclisiran Group will receive placebo on Day 180. All participants will then receive inclisiran sodium 300 mg on Day 270, which will be the third dose of inclisiran for Inclisiran Group, and the second dose of inclisiran for Control Group. All injections will be administered at the site by a healthcare professional. The EOS visit (Day 360) will be the last visit of the study.

The randomization will not be stratified.

The core part analyses will be conducted when all randomized participants have completed the visit at Day 180 (or have discontinued from the study). The final analyses will be conducted when the trial ended. No interim analyses are planned.

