### **2.4.1 Study treatment / compliance**

The number and percentage of participants receiving study dose and the injection site location will be summarized by study visit and treatment group for both core part analyses and final analyses. For core part analyses, the summary tables including Day 1 and Day 90 visit and for overall study will be provided. For final analyses, the summary table will include Day 180, and Day 270 visit using OLS.

The number of doses received during the core part (at Day 1 and Day 90), duration of exposure, patient year of exposure will be summarized by treatment group for core part analyses. Such summary table of exposure to study treatment and listing for overall study will also be provided in core part analyses. The number of doses received during the whole study, duration of exposure for overall study and patient year of exposure will be summarized by treatment group for final analyses. Listings for overall study will also be provided in final analyses.

Duration of exposure for overall study will be calculated as: minimum of (Date of last dose of treatment – Date of first dose of treatment + 1 + 180, Date of last known visit – Date of first dose of treatment + 1). Duration of exposure to study treatment for overall study will be truncated at the analysis cutoff date for core part analyses.

The number of doses received during the extension part (at Day 180 and Day 270), duration of exposure in extension part and patient year of exposure will also be summarized by treatment group using OLS for final analyses. Duration of exposure for extension part will be calculated as: minimum of (Date of last dose of treatment in extension part – Date of treatment at Day 180 + 1 + 180, Date of last known visit in extension part – Date of treatment at Day 180 + 1). If the Day 180 treatment was not taken, then the date of Day 180 visit will be used.

Patient-year of exposure will be calculated as duration of exposure/365.25.

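### The planned extension tables of injection-site reactions combine the blinded, crossed Day 180 injection with the open-label Day 270 injection, so they cannot be read per inclisiran injection

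*SAP*

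**What the plan says.** SAP 1.1 describes a crossed Day 180 injection: "participants randomized to Control Group will receive inclisiran, while participants randomized to Inclisiran Group will receive placebo on Day 180". Protocol 4.1 gives the reason: "In order to maintain the blind for the treatment group assignment, participants randomized to Control Group will receive inclisiran". For the next injection, SAP 1.1 says "Treatment on Day 270 will be open-label", with inclisiran for both groups. Protocol 1.1 gives the full sequences. Inclisiran Group: "Treated with inclisiran sodium 300mg s.c. on Day 1, Day 90 and Day 270, and with matching placebo s.c. on Day 180". Control Group: "Treated with matching placebo s.c. on Day 1 and Day 90, and with inclisiran sodium 300mg s.c. on Day 180 and Day 270".

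The study treatment allocation rule in SAP 2.1.1 assigns both the Day 180 and the Day 270 doses to the extension part. SAP 2.4.1 then summarises "The number of doses received during the extension part (at Day 180 and Day 270), duration of exposure in extension part" by treatment group, without separating inclisiran from placebo doses in that count.

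On reporting, SAP 2.7.1 tabulates extension adverse events by study part and treatment group. SAP 2.7.1.1 uses the same layout for ISRs: "The time to the first injection site reaction TEAE will also be summarized by treatment group and study part". The duration of the first ISR and the number of ISRs per participant follow it too. Overall-study ISR tables and an ISR listing are also planned, but no ISR table is laid out by injection. Time to reaction is measured in hours from the most recent injection.

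Events are assigned to parts by date. Under SAP 2.1.1 the switching date is normally the date of the Day 180 dose. Under SAP 2.7.1 an event starting on or before that date is core, and only later events are extension.

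**The concern.** Injection-site events are the only adverse drug reaction that Protocol 2.3 identifies for inclisiran, and SAP 2.7.1.1 lists them as an event of special interest. One secondary objective is the tolerability of inclisiran monotherapy during the extension.

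For that objective, the extension column of the Inclisiran Group covers one placebo and one inclisiran injection, while the Control Group column covers two inclisiran injections. Nothing in SAP 2.7.1.1 requires the columns to say so, and Protocol 6.1.3 calls the whole 180-day extension open label. Two arms with the same risk per injection can therefore show different ISR percentages, which a reader could take for an effect of repeat dosing. Each column also mixes reactions reported blind after Day 180 with reactions reported after a known inclisiran injection on Day 270. Finally, Day 180 offers a randomised, blinded comparison of local reactions to inclisiran and placebo in those still being dosed, and no planned table shows it.

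**Working it through.** **Plan figures.** The plan gives about 200 participants, 1:1, so about 100 per group. It states no ISR rate, no onset distribution and no planned test for ISRs, so there is no figure of its own to reproduce.

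**Assumed inputs (not in the documents).** p = risk of an ISR per inclisiran injection, 5% (range 2% to 8%). q = risk per placebo injection, 0.5% (range 0% to 1%). s = share of ISRs that start on the calendar date of the injection, 0 to 1. Injections are treated as independent, risk per injection is the same in both groups, and everyone receives both extension injections.

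**Step 1: what the extension column counts.** A Day 180 reaction enters it only if it starts after the Day 180 date, that is with probability q(1−s) in the Inclisiran Group and p(1−s) in the Control Group. Day 270 reactions always enter. The probability of at least one extension ISR is then:

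- Inclisiran Group: 1 − [1 − q(1−s)] × (1 − p)
- Control Group: 1 − [1 − p(1−s)] × (1 − p)

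**Step 2: p = 5%, q = 0.5%.**

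| s | Inclisiran Group | Control Group | Ratio |
|---|---|---|---|
| 0 | 1 − 0.995 × 0.95 = 5.5% | 1 − 0.95 × 0.95 = 9.75% | 0.56 |
| 0.8 | 1 − 0.999 × 0.95 = 5.1% | 1 − 0.99 × 0.95 = 5.95% | 0.86 |
| 1 | 1 − 1 × 0.95 = 5.0% | 1 − 1 × 0.95 = 5.0% | 1.0 |

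At s = 0 the ratio runs from 0.51 to 0.75 over the ranges of p and q. Every ratio below 1 arises with no true difference between the groups in risk per injection.

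**Step 3: is incidence understated in the Inclisiran Group?** Its single inclisiran injection in the extension would give 5.0%. The column shows 5.0% to 5.5%, so it is not below that. Only a rate per injection is diluted: (5% + 0.5%)/2 = 2.75% against 5%. The SAP does not report that rate.

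**Step 4: where the same-day reactions go.** They are counted in the core part. At s = 0.8, the core Control Group column becomes 1 − 0.995² × (1 − 0.8 × 0.05) = 4.96%, against 1 − 0.995² = 1.0% from its two placebo injections. A split of the extension tables alone would therefore miss most Day 180 reactions.

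**Step 5: what a Day 180 table could show.** With 100 per group, a two-sided 5% test of two proportions (normal approximation) has power 0.16 for 2% against 0.5%, 0.49 for 5% against 0.5%, and 0.67 for 8% against 1%. The comparison is descriptive.

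**The case against.** The strongest defence is that the extension columns describe what they should. The Day 180 placebo is there to keep the blind. The Inclisiran Group continues its regimen with one active injection, the Control Group starts treatment with two, and no between-group comparison in the extension is an objective. The core part already gives a randomised, blinded ISR comparison over two injections per group. SAP 2.4.1 tabulates dosing by visit, including Day 180 and Day 270, and SAP 2.1.1 defines study treatment as inclisiran or placebo. The SAP therefore does not treat every extension dose as inclisiran.

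Much of this stands, and it rules out three stronger readings that a reader might infer:

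- *The tables understate reactions in the Inclisiran Group.* The SAP reports participants with an event, and Step 3 shows that this figure is not below the expectation from one inclisiran injection.
- *A placebo comparison is lost.* The data are kept, ISRs are listed, and reaction time runs from the most recent injection, so the contrast can be derived. It is only not tabulated.
- *Day 180 gives a second placebo comparison for all adverse events.* The Inclisiran Group has by then had two inclisiran doses, so its Day 180 injection acts as placebo for local reactions only.

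The ratio of 0.56 also cannot be quoted alone. The ISR timing bins of up to 4 hours and 4 to 12 hours make same-day onset plausible, and the ratio approaches 1 as that share grows.

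The defence does not answer the point about layout. A regimen-level column still cannot show the reaction rate to an inclisiran injection. When the ratio approaches 1, it does so because the reactions to the Day 180 dose have left the extension table, while the dose itself is still counted there.

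**Conclusion.** The concern holds as a reporting weakness confined to ISRs. The documents settle the structure: two injections that differ in content and blinding share one extension column, the columns of the two groups describe different sequences, and the blinded Day 180 contrast for local reactions appears in no planned table.

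The size is not settled. The ratios of 0.56 to 1.0 rest on assumed risks of 5% and 0.5%, independent injections, full dosing and an unknown share of same-day reactions. The possibility that the difference is misread as reactions fading with repeat dosing is a judgement, not something that the documents show. The primary efficacy analysis is unaffected. The change is worth making because it is cheap and concerns the one adverse reaction already identified for the drug.

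**What to change.** In SAP 2.7.1.1, add ISR summaries by most recent injection (Day 1, Day 90, Day 180, Day 270) and by content (inclisiran or placebo), with the participants who received that injection as the denominator. Label Day 180 as blinded and Day 270 as open-label.

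In these summaries, attribute reactions that start after dosing on the Day 180 date to the Day 180 injection, and reconcile this with the switching-date and allocation rules in SAP 2.1.1 and the core and extension definitions in SAP 2.7.1. The hours-based ISR timing already planned implies that the needed times are available.

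In SAP 2.4.1, count inclisiran and placebo doses separately for the extension.

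Keep the inclisiran-versus-placebo label at Day 180 to injection-site events, and present it descriptively without a test.

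The cost is SAP wording and a few extra tables with fewer events in each. No new data are needed.
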